1. SUMMARY

Rationale:

Cancer is the second leading cause of death during the reproductive years. The long term survival improves for most cancers, reaching 80% for pediatric cancer and more than 70% for cancers in adults between 20 and 49 years of age. Early detection and improvements in cancer treatment contribute to these figures. As a result, quality of life of which preservation of fertility is one aspect, becomes more important. Fertility may however be influenced by surgery and by the gonadotoxic effects of chemo and/or radiotherapy. Therefore, fertility sparing treatments are offered to young patients in order to maintain the wish to conceive after cancer treatment. This however is associated with deviation of standard treatment and many different strategies are applied among different centers. In addition, there is a lack of studies investigating the oncological safety of these fertility sparing treatment protocols. The results of this study will enable us to better inform clinicians and patients on the efficacy of fertility sparing cancer treatment.

Objective:

To record the incidence, treatment and long term follow up of fertility preserving cancer treatment. Both the oncological and fertility outcome are recorded.

Study design: International multicentre prospective observational trial

Study population: All female adults with a cancer for whom a fertility preserving cancer treatment is applied. The results of the study population are compared to young women undergoing standard cancer treatment.

Intervention (if applicable): n.a.

Main study parameters/endpoints:

Registration of cancer diagnosis, treatment and outcome. Both the oncologic and fertility outcome are registered.

Nature and extent of the burden and risks associated with participation, benefit and group relatedness:

All patients receive fertility sparing cancer treatment on their specific request. Participation in this observational registration study is not associated with burdens or risks, since participation will not alter the treatment regimens.

2. INTRODUCTION AND RATIONALE

Never ending research in cancer treatment and optimization of prevention methods have led to increased survival rates in people diagnosed with cancer. The long term survival improves for most cancers, reaching 80% for pediatric cancers and more than 70% for cancers in adults between 20 and 49 years of age (1). As the prognosis for malignancies improves, the long-term side effects become more important. The focus has switched from a purely oncology point of view towards oncofertility, in which fertility, as one of the major factors for a good quality of life, becomes substantially more important (2).

Decreased ovarian reserve, premature ovarian insufficiency and premature menopause due to surgery and the gonadotoxic effects of chemotherapy and radiotherapy may however result in fertility impairment. As more than 60% of patients with cancer is most concerned about the impact of the treatment on their fertility, fertility sparing treatments should be offered to young patients in order to maintain the wish to conceive after cancer treatment (5).

Counselling and referring patients, who wish to safeguard their reproductive potential, to a fertility center is of great importance as up to 75% of young cancer survivors want to have children (4).

Embryo cryopreservation is the most frequently used intervention to preserve fertility, for patients undergoing a gonadotoxic treatment. Oocyte cryopreservation is less frequently used, but has a similar outcome and could be a good alternative for single women.

Other more experimental alternatives are cryopreservation of ovarian tissue, temporary translocation of the ovaries when pelvic radiotherapy is needed and ovarian function suppression with GnRH-analogues during chemotherapy (5).

Regarding cancer of the female genital tract, in which radical surgery is mostly the standard, alternatives are being investigated to preserve fertility. There are still a lot of gaps in research regarding these fertility sparing surgical treatments and the interventions are often experimental, as there is no standardized technique available due to lack of data. This leads to many different strategies being applied among different centers. In addition, there is a lack of studies investigating the oncological safety and obstetric outcome of these fertility sparing treatment protocols. Another major consequence of the absence of a standard technique is the difficulty to inform patients about the best treatment.

It is important to obtain a significant amount of cases in order to make a thorough study especially since several types of cancer do not occur regularly. It is in this respect that this study aims to fill the gap in current research.

The purpose is to enable us to obtain a significant amount of data to create more standardized fertility sparing treatment protocols and to better inform clinicians and patients on the efficacy of fertility sparing cancer treatment.

3. STUDY DESIGN

The proposed research concerns a multicenter prospective observational cohort study. European collaboration is utilized in order to include sufficient number of patients.

This is a study, for which primary approval was granted by UZ Leuven. UZ Leuven is the initiator of the study and the ethical committee of UZ Leuven is the central ethical committee. The UZ Leuven protocol is used in all centers, including the international collaborators.

3.1 Objectives

Primary Objective:

To record the incidence and oncological outcome when a fertility preserving cancer treatment is applied in young women and compare the oncological outcome with a control group.

Secondary Objective(s):

To record the incidence and fertility outcome when a fertility preserving cancer treatment is applied in young women and compare the obstetrical and neonatal outcome with the general population.

3.2 Inclusion criteria

Histological proven cancer in young women under the age of 40 for whom a fertility preserving cancer treatment is applied. For the control group, patients are eligible when they are in the fertile age but over 18 years of age and undergoing standard cancer treatment.

3.3 Sample size

We aim for at least 500 cases per tumour type + 1 control patient per study patients (resulting in 500 control patients per tumour type). This is a minimum that allows us to calculate the oncological prognosis (secondary objective).

3.4 Study procedures

In women younger than 40 years old with a cancer diagnosis for whom a fertility preserving treatment is applied, the most important oncological data will be registered, as well as information on the fertility and oncological outcome. Control patients are women who are younger than 40 years of age diagnosed with cancer and who received standard treatment. All types of cancer and all types of treatment will be registered. Patients can be included both prospectively and retrospectively. For every study patient, we include one control patient.

Recruitment of patients:

Because information on pregnant state is not available in most cancer registries prospective recruitment of patients is done as followed networking (e.g. INCIP), newsletters, presentation at conferences for obstetricians, oncologists, haematologists, and also a website for professionals (www.cancerinpregnancy.org) and for patients (<http://www.uzleuven.be/kanker-en-zwangerschap>).

We will collect the following data:

At baseline:

Oncological data include type of cancer, the date of diagnosis, tumour histology, stage of the disease, the type of treatment, cancer recurrence and survival.

Fertility data include gravidity and parity, menstrual pattern after cancer treatment, conception (artificial or natural), obstetrical complications, gestational age at delivery and mode of delivery (induction, caesarean section, spontaneous labour).

Paediatric data that will be collected include birth weight, gender, congenital malformations, admission to neonatal care unit and reason of admission.

Annually until end of study:

We will request information from the treating physician regarding patient's health status (pregnant yes/no, relapse yes/no, site of relapse, treatment of relapse, date of relapse, date of death if applicable).

This study does not involve any direct input or effort from the patient. Only the collection of existing information through the medical records is aimed for.

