8.2 Recruitment and consent

Eligible patients will be informed about the study by the supervising physician (e.g. gynaecologist, surgeon or medical oncologist) primarily treating the malignancy. The patient will also obtain written information about the study. The patient can think about participation and discuss the study with her family. They will be given enough time to consider their decision and are free to reconsider their decision at any moment during the trial. In case of participation the informed consent should be signed prior to registration of patient data. This is applicable for the prospective part of this study. An exception is made for the retrospective part of this registration study; retrospective data without the need for follow-up may be collected anonymously without a signed consent form for evaluation of quality of care since it does not fall under the scope of the WMO.

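### Section 3.4 gives no outcome-independent rule for choosing retrospectively included cases and controls, and nothing links a control to her case by stage or period of diagnosis

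*Protocol*

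**What the plan says.** Section 3.1 makes it part of the primary objective to "compare the oncological outcome with a control group". The Summary adds: "The results of the study population are compared to young women undergoing standard cancer treatment".

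The control group is described in three further places:
- Section 3.2 sets fertile age, over 18, and standard treatment.
- Section 3.3 sets the number, one control per study patient, "resulting in 500 control patients per tumour type".
- Section 3.4 sets an upper age limit of 40, standard treatment and the ratio: "For every study patient, we include one control patient".

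Section 3.4 also states: "Patients can be included both prospectively and retrospectively". That sentence covers cases as well as controls. Section 4, on the study population, has no criteria for controls.

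The items recorded would support a selection rule: "Oncological data include type of cancer, the date of diagnosis, tumour histology, stage of the disease, the type of treatment, cancer recurrence and survival".

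**The concern.** Two things are left open that are settled when a site registers a patient, not when the data are analysed.

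The first is comparability. According to the Summary, "All patients receive fertility sparing cancer treatment on their specific request". Women who ask for such treatment and are given it may differ in prognosis from women on standard treatment. No section asks that a control resemble her case in stage or period of diagnosis.

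The second is selection on outcome. When a patient is included retrospectively, relapse or death may already be in her record. If several women at a site could serve as the control, or several past cases could be entered, nothing says which to take. If relapsed women are more or less likely to be entered in one group than in the other, the comparison is biased. Stage, histology and date of diagnosis cannot correct this, because the cause of the bias is the outcome itself.

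At stake is the oncological comparison that the study was set up to provide.

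**Working it through.** **The plan's own figure.** 500 cases × 1 control = 500 controls per tumour type, which agrees with 3.3. The protocol gives no event rate or effect size, so every other input below is assumed.

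**A. Outcome known at selection.**

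Inputs: no true effect; recurrence risk R = 0.10 in both groups; a share q = 0.5 of controls is retrospective; among these, relapsed women are w times as likely to be picked; cases are not selected on outcome. Proportional hazards over a common follow-up are assumed.

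Observed control risk = q·Rw/(Rw + 1 − R) + (1 − q)·R

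HR (cases v controls) = ln(1 − 0.10)/ln(1 − control risk)

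For w = 0.5: 0.5 × 0.05/0.95 + 0.5 × 0.10 = 0.0763, and HR = ln(0.90)/ln(0.9237) = 1.33.

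| w | control risk | HR |
|---|---|---|
| 0.5 | 0.0763 | 1.33 |
| 0.8 | 0.0908 | 1.11 |
| 1 | 0.1000 | 1.00 |
| 1.25 | 0.1110 | 0.90 |
| 2 | 0.1409 | 0.69 |

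- *Retrospective share.* For w = 0.5 and w = 2 the HR is 1.14 and 0.82 with q = 0.25, and 1.95 and 0.53 with q = 1.
- *Same selection in both groups.* If cases have the same q and w, their observed risk equals that of the controls (for w = 0.5, 0.0763 in each) and the HR is 1.00. The bias needs selection that differs between the groups.
- *Stage adjustment.* Take recurrence of 5% in early and 20% in higher stage, with q = 0.5. The HR within early stage is 1.33 (w = 0.5) or 0.68 (w = 2); within higher stage it is 1.32 or 0.72. Stratifying by stage leaves the bias in place.

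**B. Stage not linked, but adjusted for.**

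SE(log HR) = √(1/d₁ + 1/d₀), where d₁ and d₀ are the events in comparable cases and controls. The multiplicative 95% half-width is exp(1.96·SE).

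*Little overlap.* All 500 cases are early stage, and so is only a share of the 500 controls; recurrence 5% in early stage, so d₁ = 25.

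| controls early | d₀ | SE | half-width |
|---|---|---|---|
| 100% | 25 | 0.283 | 1.74 |
| 70% | 17.5 | 0.312 | 1.84 |
| 50% | 12.5 | 0.346 | 1.97 |
| 30% | 7.5 | 0.416 | 2.26 |

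*Good overlap.* Cases 90% early, recurrence 5% and 20%. Summing 1/(1/d₁ + 1/d₀) over the two stages gives information of 14.89 to 17.34 as the early share among controls runs from 95% to 50%. The half-width is 1.60 to 1.66, against 1.63 when balanced at 90%.

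So lack of a stage link costs precision where overlap is poor and very little where it is good.

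**The case against.** **Stage and period can be handled in the analysis.** Matching is one option and adjustment another. The variables are collected, and a statistical analysis plan that is not shown may use them. This largely stands: with overlapping stages the loss is small (part B), and nothing in the protocol shows that overlap will be poor. It does not reach selection on outcome, because no analysis plan can change whom the sites have registered.

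**Tumour type.** A reader might infer from 3.4 alone that a control could have any cancer. Section 3.3 does not support that: one control per study patient gives 500 controls per tumour type only if controls are taken within tumour type. Section 3.4 should repeat this, but it is drafting.

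**The hazard ratios in part A are one-sided.** They assume that only controls are selected on outcome, whereas retrospective entry is open to cases too. This stands. The figures show what the text permits, not what to expect, and any remedy must cover cases as well.

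**A reader might infer that the study will favour fertility-sparing treatment.** On an unadjusted comparison with 500 per group, worse-stage controls do produce false significance in that direction. For example, with 90% of cases and 70% of controls early, and recurrence 5% and 15%, the risks are 6% and 8% and the probability of a significant result is about 0.24. That direction follows from the chosen inputs, and the calculation ignores adjustment.

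**Weak supports.** Recurrence and survival stand under the baseline heading in 3.4, but so do birth weight and other later events. The list is loosely headed and does not show that outcome is known at selection. The statement in 8.2 that "retrospective data without the need for follow-up may be collected anonymously without a signed consent form" concerns consent. The argument rests on retrospective inclusion without a selection rule.

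**Conclusion.** The point holds in limited form and should be fixed. The protocol makes a comparison with controls part of its primary objective and allows retrospective inclusion. It gives no rule that makes the entry of cases or controls independent of a known outcome, and it links a control to her case by neither stage nor period of diagnosis.

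The first gap weighs more, because differential selection on outcome cannot be repaired later. Under the assumptions of part A, moderate to strong selection of controls alone moves a true hazard ratio of 1.00 to between 1.33 and 0.69; equal selection in both groups leaves it at 1.00. The second gap can partly be met by adjustment, and its cost depends on overlap.

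The selection weights, retrospective share, recurrence rates and stage mix are all assumed. The protocol shows neither that such selection will happen nor its direction.

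**What to change.** In Section 3.4:

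1. State that retrospective cases and controls are entered by a rule that does not depend on outcome. For example: all consecutive eligible cases at a site in a stated period and, for each, the next eligible control by date of diagnosis at that site.
2. State that each control has the same tumour type as her case (making 3.3 explicit) and the same broad stage group, with a similar period of diagnosis where feasible. For rare tumours allow coarse strata, or adjustment alone.

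The cost is a few sentences and some extra site effort to find the next comparable control, which is harder in a voluntary registry and for rare tumours. Tumour type, stage and date of diagnosis are already collected, so no data items are added.

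Separate editorial note: reconcile the age wording in the Summary, 3.2, 3.4, 4.1 and 4.2. For cases, 3.2, 3.4 and 4.1 exclude age 40 while 4.2 can be read to include it. For controls, 3.2 gives a lower limit of 18 and no numeric upper limit, and 3.4 gives only the upper limit. A reader might call this a contradiction, but apart from age 40 itself the statements can be read together. One stated set of limits would settle it.

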9. ADMINISTRATIVE ASPECTS, MONITORING AND PUBLICATION

9.1 Handling and storage of data and documents

The investigator records clinical data, using a paper or electronic case report form (CRF), all data is collected in an online database that is available through www.cancerinpregnancy.org, such database being the ownership of Sponsor. Participating physicians have a personal account to log in to the registration page and access the electronic CRF. They will have permanent access only to their own series of patients. The participating physician ensures the confidentiality, accuracy, completeness, legibility and timeliness of the data recorded. Data handling and statistical analysis will be done anonymously by the investigator, with the subject identification code list only available to the local investigator (and research nurse if applicable) working in the local center. The code will be based on the birth date and center abbreviation (and not patient initials). The investigator will be the owner of the data. Data will be kept for 20 years.

Sponsor, participating physicians and sites agree and commit to handle and protect the data in accordance with the terms and provisions of all applicable data protection rules and legislation including the Belgian law of 08 December 1992 on Privacy Protection in relation to the Processing of Personal Data and the Belgian law of 22 August 2002 relating to patient's rights.

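### Within a tumour type, section 3.4 names only stage and histology as tumour prognostic factors and nothing on whether controls were suitable for fertility-sparing treatment, so the primary comparison stays open to within-stage confounding

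*Protocol*

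**What the plan says.** The primary objective in section 3.1 includes the aim to "compare the oncological outcome with a control group". Section 5.1 marks randomisation as not applicable. The summary says of the fertility-sparing group: "All patients receive fertility sparing cancer treatment on their specific request", and describes such treatment as a departure from the standard.

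Controls are defined in section 3.4: "Control patients are women who are younger than 40 years of age diagnosed with cancer and who received standard treatment". One is included per study patient. Sections 3.2 and 3.4 name no matching factor and do not require that a control could have had fertility-sparing treatment.

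Section 3.4 promises that "the most important oncological data will be registered, as well as information on the fertility and oncological outcome". The baseline list then reads: "Oncological data include type of cancer, the date of diagnosis, tumour histology, stage of the disease, the type of treatment, cancer recurrence and survival". The yearly update asks for "pregnant yes/no, relapse yes/no, site of relapse, treatment of relapse, date of relapse, date of death if applicable", which adds outcomes and their management but no prognostic factor. Section 9.1 builds the patient code from birth date and centre.

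**The concern.** The primary comparison sets women who asked for a departure from standard treatment against women who had standard treatment. In such a comparison, tumour features that influence both the choice of treatment and the relapse risk must be measured, or they distort the result. Within a tumour type, the list offers two handles on this: stage and histology. If, at the same stage and histology, lower-risk tumours more often go to fertility-sparing treatment, the fertility-sparing group will look better than it should, and a real excess of relapses could be reported as no difference.

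This is separate from the choice of analysis method. A statistical analysis plan can specify matching, weighting or regression, but only on variables that were collected. The data list is set in the protocol. The protocol's rationale is the lack of evidence on oncological safety, and its results are meant to inform patients and clinicians, so a falsely reassuring comparison would defeat its purpose.

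**Working it through.** **The plan's own figure.** Section 3.3 gives at least 500 cases and 500 controls per tumour type. It states no event rate, effect size, margin, power or follow-up, so 500 cannot be reproduced. It is taken below only as the group size.

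**Assumed inputs.** The documents give none of these. Take one unrecorded binary risk factor that varies within the same stage and histology. Its prevalence is p1 in the fertility-sparing group and p0 in controls, and it multiplies relapse risk by g. The observed relapse risk is 15% in both groups.

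**Bias factor** on the relapse risk ratio (fertility-sparing versus control):

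B = (1 + p1(g − 1)) / (1 + p0(g − 1))

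The true risk ratio that would appear as 1.00 is 1/B.

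**Precision.** With 500 × 0.15 = 75 relapses per group, the standard error of the log risk ratio is √(2 × 0.85/75) = 0.151. The 95% half-width is 1.96 × 0.1506 = 0.295.

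**Coverage** of the true value is Φ(1.96 − d) − Φ(−1.96 − d), with d = |log B|/0.1506.

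| p1 | p0 | g | B | 1/B | log B | Beyond 0.295? | Coverage |
|---|---|---|---|---|---|---|---|
| 30% | 40% | 2 | 1.3/1.4 = 0.93 | 1.08 | −0.074 | no | 92% |
| 20% | 40% | 2 | 1.2/1.4 = 0.86 | 1.17 | −0.154 | no | 82% |
| 20% | 40% | 3 | 1.4/1.8 = 0.78 | 1.29 | −0.251 | no | 61% |
| 20% | 50% | 3 | 1.4/2.0 = 0.70 | 1.43 | −0.357 | yes | 34% |

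Only in the last row does the bias exceed the half-width, so that an interval centred on its expected position misses the truth. In the other three rows that interval still contains the truth, although coverage is below the nominal 95%.

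**Effect on detecting harm.** Take a control relapse risk of 10%, a true risk ratio of 1.5, and 500 per group. Without confounding, the power at two-sided 0.05 is 66.7%. With the last row's confounder, the expected observed ratio is 1.5 × 0.70 = 1.05, and the chance of a significant result in the direction of harm falls to about 4.5%. With the milder confounder g = 2, 40% versus 50%, B = 1.4/1.5 = 0.933, the observed ratio is 1.40 and the power is 49.5%.

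**Sample size.** B contains no n. More patients narrow the interval around the biased value and leave the bias where it is.

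**The case against.** Several stronger readings are tempting, and the documents do not support them.

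- *Stage and histology are the only factors recorded.* The list is worded as what the data include, and the CRF is not shown. The protocol supports only that they are the ones named. Equally, nothing in it commits centres to more.
- *Age is missing.* Date of diagnosis is listed and the patient code rests on birth date, so age at diagnosis can probably be derived. Section 3.4 also restricts both groups to women under 40. It is enough to state age explicitly.
- *Size, nodal status, grade and margins are all omitted confounders.* Stage may carry part of size and nodal status, and histology part of grade, which reduces the residual confounding. Margin status follows from the operation. Adjusting for it could remove part of the effect under study.
- *Anything not abstracted now is lost.* The source is existing medical records and the local centre holds the code list, so coded patients can be abstracted again. The loss is likely to be permanent mainly for the retrospective data that section 8.2 allows to be collected anonymously.
- *The protocol shows selection of low-risk tumours.* It describes selection by the patient's wish. Selection on tumour risk is an inference. The introduction also covers embryo and oocyte cryopreservation, where selection within a stage is less obvious.
- *The interval would exclude the truth.* That holds for one of the four scenarios, and a 20% versus 50% imbalance in a threefold risk factor after conditioning on stage and histology has no support in the documents.

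What remains is that no within-stage risk feature and no record of control suitability is named for a non-randomised primary comparison.

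**Conclusion.** The point holds as a conditional weakness in the data list. If selection within stage operates, analysis on the named items leaves residual confounding that neither adjustment nor a larger sample removes. A sensitivity analysis can bound it but cannot eliminate it. Over the assumed range, a true relapse risk 8% to 43% higher would be reported as no difference. Whether any such bias exists, and how large it is, cannot be read from the protocol, because every prevalence, relative risk and relapse risk used here is assumed. If selection ran the other way, the comparison would still be confounded, with the sign reversed. The change is worth making because it is cheap and bears directly on the primary comparison.

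**What to change.** In section 3.4:

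1. Add a short set of pre-treatment prognostic items from existing records to the baseline list: tumour size, grade and nodal status where they apply to the tumour type and are not already captured by stage, plus one or two markers specific to the tumour type. State age at diagnosis explicitly. Do not use margin status as an adjustment variable.
2. Add one field for each control: suitable for fertility-sparing treatment by the centre's own criteria (yes / no / unknown), with the reason standard treatment was given.
3. Use these items in the primary comparison, repeat it in controls marked suitable, and report a sensitivity analysis for unmeasured confounding.

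The cost is a few more eCRF fields from records already being read, and a protocol amendment. Some values will be missing in retrospective patients, especially those collected anonymously. No patient's treatment changes.

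### Annual pregnancy follow-up names only the treating physician and existing records, so pregnancies managed elsewhere may be missed and the secondary fertility outcome biased low

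*Protocol*

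**What the plan says.** Section 3.1 makes the fertility outcome a secondary objective and adds the aim to "compare the obstetrical and neonatal outcome with the general population".

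Section 3.4 sets the follow-up. Under the heading "Annually until end of study" it states: "We will request information from the treating physician regarding patient's health status (pregnant yes/no". The rest of that list covers relapse and death. Two sentences then limit the sources: "This study does not involve any direct input or effort from the patient" and "Only the collection of existing information through the medical records is aimed for". Section 3.4 does not say which records are meant, or who the treating physician is.

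The nearest description of that person is in section 8.2, on who informs eligible patients: the "supervising physician (e.g. gynaecologist, surgeon or medical oncologist) primarily treating the malignancy".

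The detailed reproductive items, such as "conception (artificial or natural), obstetrical complications, gestational age at delivery and mode of delivery", and the newborn items are listed in 3.4 under baseline. The annual list has none of them.

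**The concern.** An annual query about cancer status and one about pregnancy need not be equally well answered by the same person. A physician who sees a woman every year for her cancer can report relapse fully, yet have no record of a conception, early loss or birth handled by another service. Section 3.4 registers all cancer types, so in some tumour groups that physician may have little to do with reproductive care. This differs from loss to cancer follow-up: the woman is still under observation, but part of her outcome is not.

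The conception share in the secondary objective is at stake, and with it possibly the obstetric and neonatal comparison. No later analysis can recover a pregnancy that was never collected, so this belongs in the data-collection section of the protocol and cannot be left to an analysis plan.

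**Working it through.** **What can be reproduced.** The only design figure is in section 3.3: "We aim for at least 500 cases per tumour type + 1 control patient per study patients". It comes with no pregnancy rate, effect size or completeness assumption, so it cannot be re-derived for this endpoint. It is used below only as a scale. All rates that follow are assumptions.

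**1. Conception share.** Observed share = true share × proportion captured. Take a true share of 30%, which is 150 of 500 women.

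| Captured | Observed share | Women missed per 500 |
|---|---|---|
| 90% | 0.30 × 0.90 = 27% | 15 |
| 80% | 0.30 × 0.80 = 24% | 30 |
| 70% | 0.30 × 0.70 = 21% | 45 |
| 60% | 0.30 × 0.60 = 18% | 60 |

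At 80% capture, true shares of 20% to 50% give 20 to 50 women missed per 500. The direction is always downward.

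**2. Complication share among captured pregnancies.** Let c be the true share complicated, and s_c and s_u the capture of complicated and uncomplicated pregnancies. Observed share = c·s_c / (c·s_c + (1 − c)·s_u). Take c = 10%.

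| s_c | s_u | Observed share |
|---|---|---|
| 80% | 80% | 0.080 / (0.080 + 0.720) = 10.0% |
| 90% | 75% | 0.090 / (0.090 + 0.675) = 11.8% |
| 90% | 60% | 0.090 / (0.090 + 0.540) = 14.3% |

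Equal capture leaves the rate unchanged. A shift appears only when capture is differential.

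**3. Effect on the planned test.** Section 6 names an exact binomial test against an expected value, at a significance level of 0.05. With 150 true pregnancies and a true 10% equal to the reference, the probability of wrongly rejecting is:

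- 4.6% at 80%/80% capture (120 captured);
- 12.6% at 90%/70% (108 captured);
- 26.4% at 90%/60% (about 94 captured).

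**4. The wording of the item.** If pregnant yes/no is read as status on the day of the query, even a fully informed physician misses pregnancies that fall between queries. A 40-week pregnancy spans a yearly query at a random date with probability 40/52 = 77%, and a 10-week loss with probability 10/52 = 19%. The protocol does not say whether current status or the whole interval is meant.

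**The case against.** The strongest reply is that the protocol does not confine the source to oncology. Section 3.4 says only the treating physician, undefined. Section 8.2 concerns recruitment, and its first example is a gynaecologist. The medical records in 3.4 are not limited to cancer records, and items such as gestational age and neonatal admission suggest that obstetric records were expected to be reachable. The case report form is not shown and may hold an 'unknown' code. The primary objective is oncological and unaffected.

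Much of this stands, and it rules out three stronger readings:

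- A reader might infer that only the physician treating the cancer is asked. That joins 3.4 to 8.2; neither section says it of the annual query.
- A reader might infer that missed pregnancies are recorded as 'no'. The text does not say so; they could equally be left blank.
- A reader might infer that complicated pregnancies are over-represented. No section supports this, and equal capture produces none.

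The reply does not remove the gap. Unspecified records are not a route to a maternity unit or fertility centre elsewhere, and patient input is expressly excluded. A physician who does not know of a pregnancy has no described way to find out or to say so.

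**Conclusion.** The point holds as an unaddressed risk of under-counting pregnancies in the secondary objective. That follows from what 3.4 names and excludes, and does not depend on complicated pregnancies being captured better than others. The bias in the obstetric comparison is conditional on such differential capture.

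The sizes are illustrations. At 60-80% capture, a true 30% conception share would be reported as 18-24%, or 60 to 30 women missed per 500. A true 10% complication rate would be reported as 11.8-14.3% only with 90% against 75-60% capture. The protocol supplies none of these rates. Nor does it show that capture differs by tumour type; that is a reason to report completeness by type, not an established bias.

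The change is worth making because it is cheap and must come before the data are collected. It does not touch the primary objective.

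**What to change.** In section 3.4:

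- Change the annual item to pregnant since last contact, yes/no/unknown, with a field for the source of the answer.
- For prospectively consented women, record at consent a gynaecologist, fertility centre or general practitioner whom the site may ask for the fertility items when the treating physician answers 'unknown'.
- State that 'unknown' is not counted as 'no'.
- Report completeness of pregnancy status by tumour type and source, with a sensitivity analysis over the unknowns.

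Do not restrict the fertility results to women who have a reproductive source, because that selects on the outcome. If, as an assumption, 90% of women who conceive and 50% of those who do not have such a source, a true 30% becomes 0.30 × 0.90 / (0.30 × 0.90 + 0.70 × 0.50) = 0.27 / (0.27 + 0.35) = 43.5%. A yearly form for the woman is not proposed either, since it would reverse the stated choice to ask nothing of patients.

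The cost is a line in the consent form, two changes to the case report form and some extra requests by sites. Two limits remain. Retrospective patients included without consent (section 8.2) have no named contact, so nothing is remedied for them. A physician who confidently but wrongly answers 'no' will not trigger a request; the source field only makes such answers visible.
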